WMO Medical Research Involving Human Subjects Act; in Dutch: Wet Medisch-

wetenschappelijk Onderzoek met Mensen

Ga Gallium-68AE Adverse EventAR Adverse Reaction

CT Computed Tomography IB Investigator's Brochure

METC Medical research ethics committee (MREC); in Dutch: medisch ethische

toetsing commissie (METC)

MRI Magnetic Resonance Imaging

mSv MilliSievert
PCa Prostate Cancer

PERCIST PET Response Evaluation Criteria In Solid Tumours

PET Positron Emission Tomography

PET-based MaNagement of Metastasized prostate cancer treated with

MaN Novel therapies

PSA Prostate-Specific Antigen.

PSMA Prostate-Specific Membrane Antigen

RECIST Response Evaluation Criteria in Solid Tumours

(S)AE (Serious) Adverse Event

SUSAR Suspected Unexpected Serious Adverse Reaction

WMO Medical Research Involving Human Subjects Act (in Dutch: Wet Medisch-

wetenschappelijk Onderzoek met Mensen

SUMMARY

Rationale: Men, newly diagnosed with metastasized prostate cancer on PSMA PET/CT, who start on standard hormonal therapy, are additionally treated with either upfront chemotherapy or upfront extra androgen-receptor targeted agents ('ARTA'), as per guidelines' recommendations. The benefit in overall survival of these two options is similar, but important differences exist in patient-specific efficacy, costs, side-effects, and impact on quality of life. No predictive factors are available to individualize treatment choice. Currently, a one-size-fits-all strategy with hormonal therapy plus chemotherapy is usually followed.

Objective: To assess the predictive value of early response measurements on PSMA-PET/CT for therapy success, defined as time to development of castration-resistant prostate cancer (CRPC), in order to personalize treatment choice.

Study design: Prospective, single arm, open label, non-interventional, non-therapeutic observational cohort study.

Study population: Patients >18 years with newly diagnosed, histologically proven prostate cancer with >3 skeletal or visceral metastatic lesions on the PSMA-PET/CT, who are considered eligible for upfront therapy (chemotherapy or ARTA) in addition to standard hormonal therapy.

Main study parameters/endpoints:

Primary parameter: Predictive value of early response on PSMA-PET/CT to upfront therapy, according to PERCIST criteria. Primary endpoint: Time to development of CRPC. Secondary parameters: Predictive value of early response on PSMA-PET/CT to hormonal therapy; predictive value of baseline PSMA-PET/CT, analysis of response in different subgroups of patients: e.g. high versus low tumour load, high versus low PSA, high versus low Gleason score. Secondary endpoint: Time to initiation of second line therapy after castration-resistant disease has been found.

Nature and extent of the burden and risks associated with participation, benefit, and group relatedness:

Patients will be treated according to standard of care, including baseline PSMA-PET/CT. The timing of follow-up PSMA-PET/CT imaging will be standardized. Instead of imaging at biochemical or clinical signs of disease progression, one PSMA-PET/CT will be performed after two months of hormonal therapy, one PSMA-PET/CT will be performed after two months of upfront therapy. Each PSMA-PET/CT scan will require an extra visit (2-3 hours) and a limited radiation burden after intravenous injection of PSMA. The additional information from the standardized follow-up PSMA-PET/CT scans will not be used for clinical decision-making.

1. INTRODUCTION AND RATIONALE

In men with newly diagnosed metastasized prostate cancer (i.e. metastatic hormone-sensitive prostate cancer; M+HSPC) who start on androgen deprivation therapy, a personalized approach towards choosing upfront additional therapy is required. PSMA-PET/CT early response has the potential to stratify patients who will best respond to chemotherapy or androgen-receptor targeted agents (ARTA).

In 2019, 15% of 13,000 prostate cancer (PCa) diagnoses in The Netherlands was already in the metastasized stage at first detection (~1,950 cases/year).(IKNL 2020) In M+HSPC, palliative androgen-deprivation therapy (ADT) is the backbone of therapy, usually a LHRH agonist.(Cornford 2019) The condition and associated treatments have a detrimental impact on quality of life (QoL).(Holm 2018) In recent years, different therapies have been found to have a favourable impact on overall survival (OS) when initiated directly upfront (which should be started <3 months after diagnosis) in combination with ADT, revolutionizing treatment for M+HSPC. These options include very different types of agents; chemotherapy (i.e. docetaxel) or novel androgen-receptor targeted agents (ARTA; such as: CYP-17 inhibitor: abiraterone, or competitive inhibitors of the androgen-receptor: apalutamide, enzalutamide).(James 2016, Sweeney 2015, James 2017, Fizazi 2017, Chi 2019, Davis 2019, Armstrong 2019). Although the favourable effect on OS of these drugs when added to ADT monotherapy is similar in the M+HSPC setting on a group level (docetaxel chemotherapy: hazard ratio OS 0.61-0.78; ARTA: hazard ratio 0.62-0.67), there are important differences in costs, treatment burden, side-effects, and impact on QoL.(Hird 2020) Also, the choice for a specific therapy in first line for M+HSPC influences the effectiveness of treatments when the castration-resistant phase of PCa (CRPC) is reached (after median 18 months).(deWit 2020) Currently, docetaxel chemotherapy is mostly used as a first line treatment in addition to ADT.(Kuppen 2019)

For the individual M+HSPC patient, the response to chemotherapy or ARTA is highly variable. A possible explanation may be the heterogeneity in androgen-receptor mutations. (Bostwick 1998, Evans 2011) One man may benefit more from ADT plus upfront chemotherapy, the other may be better off with ADT plus additional hormonal manipulation with an ARTA. Basic research on biomarkers for response in this setting (e.g. AR-V7; androgen receptor variant 7) have failed to translate to use in clinical practice.(Antonarakis 2014) Thus, there is a lack of predictive factors providing individualized guidance (e.g. which first line upfront therapy and in which order). Currently, a blind, one-size-fits-all strategy is usually attempted first. Furthermore, there is no standard approach regarding imaging (skeletal scintigraphy, CT, and/or PET-imaging) at diagnosis or follow-up of M+HSPC patients. This is highly variable, depending on hospital and physician preference.(Mottet 2017)

Prostate-specific membrane antigen (PSMA)-PET/CT imaging has revolutionized PCa nodal and distant metastasis staging, initially in the recurrent disease setting after local surgery or radiation therapy, but also increasingly in the primary setting.(Hofman 2020, Perera 2020) This type of PET imaging is specific for PCa. PSMA tracer uptake may be associated with the same tumour features that are related to the susceptibility of disease to ADT and additional upfront chemotherapy, or additional androgen receptor manipulation with an ARTA.(Bostwick 1998, Evans 2011) In other tumour types (e.g. lymphoma or bladder

cancer), PET imaging is used to assess treatment response to (neo-adjuvant) chemotherapy.(Witjes 2020) Essential decisions on continuation, early discontinuation, or switch of treatment are made based on these imaging results. Currently, the type (e.g. CT/MRI, skeletal scintigraphy or PET-imaging) and timing of imaging in M+HSPC patients is not standardized, but variable dependent on hospital and physician preference.(Cornford 2017)

With the current availability of a PCa specific imaging modality, access to very different types of upfront therapy (chemotherapy versus ARTA) added to standard ADT, the potential of imaging-based early treatment response to individualise treatment in M+HSPC patients, needs to be explored. Risk stratification may improve timing and sequencing of the available upfront therapy options, reducing unnecessary therapies and concomitant impact on QoL.

Results of the study can be used to move from the current paradigm of using biochemical (PSA) and clinical (symptoms) parameters to guide imaging and treatment decisions, to a standardized imaging-based follow-up strategy in order to individualize treatment timing and sequencing. Future options for this study approach include a randomized setting for upfront treatment options.

[figure not shown]
2. OBJECTIVES

The primary objective of the current research proposal is to assess whether PSMA-PET/CT early response assessment (between start of upfront therapy and after 2 months of upfront therapy) is associated with treatment success (defined as time to development of CRPC). This may allow for individualized treatment planning in newly diagnosed M+ HSPC patients, who have started on ADT and receive additional upfront therapy (Figure 1).

By performing PSMA PET/CT at fixed time points during ADT and upfront therapy treatment, information is collected on the imaging–based response to treatment. Analysis of the value of PSMA-PET/CT will be assessed by predictive modelling, taking the following predictive factors into account: PET findings, PSA at diagnosis, pathological Gleason score, tumour load, and PSA early response.

The secondary objectives include:

- Predictive value of baseline PSMA-PET/CT imaging on time to development of CRPC.
- Predictive value of early response to ADT only (which is standard of care during first 2-3 months of therapy; upfront therapy needs to be started within this timeframe) on time to development of CRPC.
- Analysis of response in different subgroups of patients: high versus low tumour load, high versus low PSA, high versus low Gleason score, <median versus >median age at diagnosis.

* Primary predictor: Upfront therapy PSMA response

Fig. 1 PET-MaN study design. (SOC = standard of care) Imaging will include PSMA-PET/CT at standardized time points (instead of at progression / on indication only): 1st baseline, 2nd after 2 months of hormonal therapy (ADT), and 3rd after 2 months of upfront therapy (for docetaxel, this is between 3rd and 4th cycle (out of 6)).

3. STUDY DESIGN

The study is a prospective open-label, non-interventional, non-therapeutic observational cohort study. The study is performed in an outpatient setting. Total study duration will be 48 months.

Multicenter (Netherlands):

- UMC Utrecht, Utrecht (lead);
- St Antonius Hospital, Utrecht / Nieuwegein (external inclusion);
- Meander MC, Amersfoort (external inclusion);
- Amsterdam UMC, Amsterdam (external inclusion).

Patients will be treated with hormonal therapy plus upfront therapy. Indication for upfront therapy and the choice for specific combination will be made at a multidisciplinary meeting. Patients are elected for study participation after prostate cancer has been histologically confirmed and signs of multiple metastases have been confirmed on PSMA-PET/CT-imaging. The definition of multiple / high volume metastasis is: >3 metastatic lesions (any combination of either lymph node metastasis outside of pelvis, bone metastasis, or visceral metastasis). Participating centers will standard use PSMA PET/CT as first imaging choice at suspicion of metastasized disease.

Standardized imaging (Figure 1):

- PSMA-PET/CT:
 - 1. Standard of care PSMA PET/CT: At diagnosis (hormonal therapy needs to be started <4 weeks).
 - 2. Additional PSMA PET/CT: 2 months after start hormonal therapy (+/- 1 week).
 - 3. Additional PSMA PET/CT: 2 months after start of chemotherapy (+/- 1 week).

Patients continue hormonal therapy plus upfront therapy according to standard of care. Follow-up of standard of care consists of monthly outpatient checks, including standard lab tests (i.e. PSA, AF, testosterone, electrolytes, full blood count).

The results of the additional PSMA-PET/CT scans will not be blinded to patients or physicians and will not be used in clinical decision-making.

The primary endpoint is time from start of ADT to CRPC. CRPC is defined by EAU guidelines (Cornford 2020) as:

Castrate serum testosterone <50 ng/dL or 1.7 nmol/L plus either:

- a. Biochemical progression: Three consecutive rises in PSA at least one week apart resulting in two 50% increases over the nadir, and a PSA >2 ng/mL, or:
- b. Radiological progression: The appearance of new lesions: either two or more new bone lesions on skeletal scintigraphy or a soft tissue lesion on CT using RECIST (Response Evaluation Criteria in Solid Tumours) or on (PSMA-)PET/CT-imaging using PERCIST (PET Response Evaluation Criteria In Solid Tumours) (Fanti 2020, Boellaard 2015).

(Symptomatic progression alone must be questioned and subject to further investigation. It is not sufficient to diagnose CRPC.)

In case of biochemical, radiological, or clinical progression indicating development of castration-resistant disease (CRPC), next line therapy will be considered at a multidisciplinary meeting, according to standard of care.

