5. METHODS

5.1 Study parameters/endpoints

5.1.1 Main study parameter/endpoint

Main parameter:

- Response to upfront therapy on PSMA-PET/CT based on PERCIST (PET Response Criteria In Solid Tumours).

PERCIST consists of a set of rules to interpretate solid tumor response on the PET/CT originally based on the FDG-PET/CT (O 2016, Fanti 2019). It looks at the tumor uptake of the PET tracer also expressed as the standardized uptake value (SUV). It divides tumor response based on the perceptual change in SUV between two (in our case) PSMA PET/CT's and the change in the amount of tumor lesions (see table 1). For the notation you also need to include the amount of time between the two PET scans. For example (35% increase, 4 weeks, five new lesions).

Table 1

Response	PSMA PET/CT interpretation
Complete response (CR)	Complete resolution of PSMA-tracer uptake in all
	lesions
Partial response (PR)	More than or equal to 30% reduction of SUV and an
	absolute drop of 0.8 SUV units
Progressive disease (PD)	More than or equal to 30% increase in SUV and
	absolute increase of 0.8 SUV units, or appearance of
	new lesions with PSMA-tracer uptake
Stable disease (SD)	Not quality for CR, PR, or PD

NB: lesions with prior radiation treatment (e.g. symptomatic bone metastasis) will not be accounted for in the PERCIST response evaluation.

Main endpoint:

- Time since start ADT to development of castration-resistant disease (CRPC). CRPC is defined by EAU guidelines (Cornford 2020) as:

Castrate serum testosterone <50 ng/dL or 1.7 nmol/L plus either:

- a. Biochemical progression: Three consecutive rises in PSA at least one week apart, resulting in two 50% increases over the nadir, and a PSA >2 ng/mL, or:
- b. Radiological progression: The appearance of new lesions: either two or more new bone lesions on skeletal scintigraphy or a soft tissue lesion on CT using RECIST (Response Evaluation Criteria in Solid Tumours) or on (PSMA-)PET/CT-imaging using PERCIST (PET Response Evaluation Criteria In Solid Tumours) (Fanti 2020, Boellaard 2015).

Symptomatic progression alone must be questioned and subject to further investigation. It is not sufficient to diagnose CRPC.

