5.2.1 PSMA-PET/CT imaging protocol

PSMA-PET/CT will be performed according to standard of care, with low-dose CT using 1.5-2.0 MBq/kg of PSMA-tracer (68-Gallium PSMA and 18 Fluor PSMA are allowed). Image reconstruction will be performed according to EARL accreditation.(Boellaard 2015) The used PSMA tracer may vary between participating centers, but in each center the same tracer will be used at baseline and during follow-up. Image acquisition starts 60 minutes (+/- 15 minutes is acceptable) after injection from head to upper thigh. Effective absorbed dose is approximately 6 mSv, which is similar to a full-dose CT scan of the abdomen. IV drip is necessary to inject the tracer.

The scans will be examine by the local nuclear medicine physician and afterwards two experienced nuclear medicine physicians will examine all PSMA-PET/CT images. The following parameters will be assessed:

- TNM stage.
- Response according to PERCIST (in follow-up scans).
- PiP-RADS scores.
- Location and number of prostate lesions, lymph node metastases and distant metastases.
- Activity (SUVIbm-mean, SUVIbm-peak, SUVIbm-max) of all lesions.

5.2.1.1 Timing first PSMA-PET/CT – baseline First PSMA-PET/CT needs to be performed <4 weeks before start ADT.

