8.3 Benefits and risks assessment, group relatedness

Standard introduction of PSMA-PET/CT into the diagnostic and follow-up process may result in more accurate visualization of true tumour and metastasis status and assessment of disease response, but will not impact therapy choice or other disease management changes in this study. Participating patients will not benefit from the results of this study.

For the PSMA PET/CT an IV need to be placed to administer the radioligand. The whole procedure will take 1,5 hours and patients will be exposed to 6,4 mSV effective dose each time. Therefore, subjects in this study will have an additional radiation exposure of a total of 12,8 mSV. This amount can be considered negligible and the burden can be considered minimal as we aim to plan the PSMA PET/CT during regular follow-up moments at the clinic and thereby minimize the amount of travel.

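### One finding on an open study scan can be both the primary predictor and the CRPC event, and the statement that these scans are not used in decisions is not secured

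*Combined protocol and SAP*

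**What the plan says.** Section 3 adds two PSMA-PET/CT scans to the baseline scan: scan 2 after two months of hormonal therapy and scan 3 after two months of upfront therapy. On access and use it states: "The results of the additional PSMA-PET/CT scans will not be blinded to patients or physicians and will not be used in clinical decision-making". The Summary repeats that the extra scans play no part in decisions. Section 8.3 says that PSMA-PET/CT "will not impact therapy choice or other disease management changes in this study".

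The primary endpoint is time from start of hormonal therapy to CRPC (sections 3 and 5.1.1). CRPC requires "Castrate serum testosterone <50 ng/dL or 1.7 nmol/L plus either" biochemical or radiological progression. The radiological branch, criterion b, is the appearance of new lesions and accepts findings on scintigraphy, on CT, "or on (PSMA-)PET/CT-imaging using PERCIST". Neither section excludes scans 2 and 3.

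The primary predictor is the PERCIST response at scan 3. In Table 1 (section 5.1.1), PD includes the appearance of "new lesions with PSMA-tracer uptake".

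Section 3 also says that when progression, including radiological progression, indicates CRPC, "next line therapy will be considered at a multidisciplinary meeting, according to standard of care". Section 7.1 tests the predictor with a likelihood ratio test of two Cox models, with and without it. No landmark at scan 3 is defined. On reading, section 5.2.1 says that, after the local read, "two experienced nuclear medicine physicians will examine all PSMA-PET/CT images". It does not say what those readers may know about the patient's course.

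**The concern.** A predictor should be measured independently of the outcome it predicts. Here the two share a component. If a castrate man has a qualifying new lesion on scan 3, that lesion makes him PD in the predictor and, on the same day, meets criterion b. The Cox model then credits scan 3 with predicting an event that scan 3 itself recorded.

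There is a second, separate problem. Treating physicians see the scans, and radiological progression leads to a discussion of next-line therapy. The plan contains nothing that puts the no-use statement into effect: no rule for a study scan that shows progression, and no record of what followed from it. Section 5.7 even calls the two extra scans standard of care, which makes it harder to see how standard-of-care management would leave them aside.

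At stake is the study's main conclusion, which is whether the scan-3 response adds to the six known predictors.

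**Working it through.** **1. The passages side by side**

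- Predictor: a new PSMA-avid lesion at scan 3 is PD (Table 1).
- Event: castrate testosterone plus a new lesion accepted under criterion b is CRPC (sections 3 and 5.1.1). Testosterone is among the monthly laboratory checks in section 3, so the castrate condition can be assessed around the time of the scan.
- Clock: time starts at hormonal therapy, before scan 3, so such an event enters the primary test. By the same rule, a new lesion on scan 2 could date CRPC before the primary predictor has been measured.
- Consequence: section 3 has next-line therapy considered on radiological progression. Section 3 (on use), section 8.3 and the Summary say the scans do not enter decisions or management.

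**2. Planning figures used as inputs**

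The sample size part of section 4.2 gives N = 150, event probability 0.5 (150 × 0.5 = 75 events), SD 4 per 10 percentage points, R² 0.75, hazard ratio (HR) 1.2-1.3 and two-sided 5%. The score-test formula is

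D = (1.960 + 0.842)² / [SD² × ln(HR)² × (1 − R²)], N = D / 0.5.

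- SD 4, R² 0.75, HR 1.2: 7.849 / (16 × 0.03324 × 0.25) = 59.0 events, N = 119.
- SD 4, R² 0.80, HR 1.2: 7.849 / (16 × 0.03324 × 0.20) = 73.8 events, N = 148.

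So 150 is reproduced with R² 0.80, the other end of the range in the Figure 2 caption, and not with 0.75. That is a separate matter. I use N = 150 and R² 0.75 below.

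**3. Size of the incorporation effect when there is no true effect**

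These are simulated trials with true HR 1.0, follow-up to 24 months and about 75 events. Two inputs are assumptions. Scan 3 is placed at 4.5 months; the documents imply between 2 + 2 = 4 and 3 + 2 = 5 months. The share of patients coded as CRPC at scan 3 is set at 3%, 5% or 10%, because the documents give no PD rate. The table shows how often the nominal 5% test rejects.

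| How scan-3 events relate to the predictor | 3% | 5% | 10% |
|---|---|---|---|
| Continuous SUV change, new lesions unrelated to it | 4-5% | 4-5% | 4-5% |
| Continuous, events in the worst raw changes | 11% | 21% | 55% |
| Continuous, events in the worst covariate-adjusted changes | 22% | 57% | 94% |
| PD as a category | 100% | 100% | 100% |

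Other set-ups for the second row gave results as low as 8%, 11% and 27%, so the size depends heavily on modelling choices. When no scan-3 finding is counted as an event, rejection is 5-6%.

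On the HR scale, take residual SD 4 × √(1 − 0.75) = 2 and the covariate-adjusted tail. Coding 2%, 5% or 10% of patients turns a true HR of 1.0 into 1.05, 1.15 or 1.28, and a true 1.2 into 1.26, 1.37 or 1.52. A spurious 1.28 lies inside the 1.2-1.3 range the study was sized to detect.

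**4. The opposite direction**

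Suppose physicians act on the scan, and this multiplies the hazard by 0.8 to 0.6 in the worst 10-20% of patients. A true HR of 1.2 is then estimated at 1.18 to 1.11. With 2% of patients coded as CRPC at scan 3 and hazard × 0.6 in the worst 20%, the two effects partly cancel and 1.2 becomes 1.17.

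**The case against.** The strongest reply has four parts.

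First, a reader might infer that the protocol contradicts itself by saying a study scan cannot set the endpoint date. It does not say that. Section 3 and section 8.3 exclude the scans from decisions and management and are silent on dating CRPC. The overlap of predictor and endpoint comes from the definitions, not from a broken promise.

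Second, a reader might infer that the no-use statement is false. The documents do not show that either. The rule on next-line therapy is general and can be read as covering progression found in routine care, with the study scans as a specific exception. What stands is that the exception is not written into that rule, nothing enforces it, and the physicians see the results.

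Third, a reader might infer that the primary association is biased upward as a matter of fact. Incorporation does push upward, but treatment changes prompted by an open scan push downward, so the net sign is not fixed.

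Fourth, criterion b concerns new lesions and does not name a rise in SUV. Its wording can also be read as limiting the PET route to soft-tissue lesions. The sample size treats the predictor as a continuous percentage change. If that is the analysed form and new lesions are unrelated to it, there is no inflation. This is correct, and the first row of the table shows it. But the same section lists the predictor as the four PERCIST categories, and under that form even a few cases suffice: 3 of 150 patients (2%) gave rejection in over 99% of simulated null trials. The narrow reading of criterion b reduces the overlap without removing it.

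**Conclusion.** The point stands as a defect in the endpoint rule: as written, one scan-3 finding can be both predictor and event, and nothing in the plan blocks this. It can inflate the primary test. How far is unknown, because the documents give neither a PD rate nor a rate of treatment change. With an assumed 3-10% of patients coded as CRPC at scan 3 and no true effect, rejection runs from about 5%, through roughly 10-95%, to near 100%, depending on whether new lesions track the SUV change and on whether the predictor is continuous or categorical. No single figure from that range should be quoted as the magnitude.

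The no-use statements are unsecured and in tension with the rule on next-line therapy. They are not disproved, and the net direction of bias cannot be settled from the documents. The change should be made because it is cheap and removes the incorporation route whichever assumption is right.

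**What to change.** - State in sections 3 and 5.1.1 that scans 2 and 3 cannot by themselves establish or date CRPC in the primary analysis.
- Prespecify a sensitivity endpoint that uses only the PSA-plus-testosterone criterion, dated from the monthly laboratory checks already planned. It is less sensitive to the open scan but not immune, since a therapy change prompted by the scan would also alter PSA.
- Have the planned two-physician read supply the PERCIST response for the model, made without knowledge of later PSA or CRPC status. The local read can stay open.
- Record any work-up or therapy change that follows a study scan.
- Reconcile the no-use statements (Summary, sections 3 and 8.3) with the rule on next-line therapy in section 3 and with section 5.7. Which clinical rule applies is for the sponsor to decide.

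The cost is some endpoint wording, one sensitivity analysis, one case report form item and an instruction to readers who are already planned. The downside is that progressions seen only on study scans are dated later, and the PSA-based endpoint misses progression without a PSA rise.
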